#### **Chest wall target volumes post-mastectomy**

- *Mastectomy Scar*: Around the mastectomy scar is a common location for chest wall recurrences post-mastectomy. To help reproducibility in the design and evaluation of post-mastectomy radiotherapy treatment plans, an initial clinical target volume for the mastectomy scar will be created. The Mastectomy Scar will first be contoured by delineating the radiopaque wire placed over the scar at CT simulation as a surrogate of the scar and including any visible postoperative changes on CT in the subcutaneous tissue deep to the wire per the investigator's discretion.
- *Mastectomy Scar CTV*: Mastectomy Scar and associated surgical change + 1 cm 3D expansion. Limit the CTV expansion posteriorly at anterior surface of the ribs or expander/implant (if present) and anterolaterally at skin. This structure should not cross midline.
- *Mastectomy Scar PTV*: Mastectomy Scar CTV + 7 mm 3D expansion (excludes heart).
- *Mastectomy Scar PTV Eval*: Since a substantial part of the Mastectomy Scar PTV extends outside the patient – a Mastectomy Scar PTV Eval is created. This Mastectomy Scar PTV Eval is limited to exclude the part that extends outside the ipsilateral body/chest wall and the first 3 mm of tissue under the skin (in order to remove some of the buildup region for the DVH analysis) and posteriorly is limited to exclude lung and heart. The Mastectomy Scar PTV Eval should not cross midline and should be contained within the borders of the Chest wall PTV Eval. This is the structure used for DVH constraints, analysis, and compliance. (*NOTE: Occasionally, the Mastectomy Scar location will lead to a CTV and PTV Eval that does cross midline. The investigator will have to assess clinically whether adequate radiation can be delivered if the Mastectomy Scar CTV and PTV Eval is truncated at midline. If it is felt that the Mastectomy Scar CTV and PTV Eval must cross midline – this case may have significant challenges in meeting Compliance Criteria for this protocol and might not be suitable for enrollment.*)
- *Chest wall CTV*: Includes the Mastectomy Scar CTV, and takes into account the radiopaque markers placed at CT identifying clinical extent of chest wall, surgical changes visualized by CT, and consensus definitions of anatomical borders of chest wall from the RTOG Breast Cancer Atlas <http://www.rtog.org/CoreLab/ContouringAtlases/BreastCancerAtlas.aspx>. The Chest wall CTV will encompass the any reconstruction (expander/implant/flap) if present, and is limited by the skin anteriorly and should not extend deeper than the ribs so that it excludes the lung and heart. Depending on the location of the Mastectomy Scar CTV, it should exclude the sternum medially and the axilla deep to anterior surface of the pectoralis major muscle laterally. In general, the chest wall CTV should not cross midline.
- Expanders, implants or autologous tissue present for reconstruction will be included in the Chest wall CTV. The degree of expander expansion present is per the treating physician's discretion. The expander should remain at the same expansion through the course of treatment that is present for the CT simulation.

- *Chest wall PTV*: Chest wall CTV + 7 mm 3D expansion (excludes heart and does not cross midline).
- *Chest wall PTV Eval*: As a part of the Chest wall PTV often extends outside the patient, the Chest wall PTV is then copied to a Chest wall PTV Eval which is edited. This Chest wall PTV Eval is limited anteriorly to exclude the part outside the patient and the first 3 mm of tissue under the skin (in order to remove some of the buildup region for the DVH analysis) and posteriorly is limited to no deeper than the posterior rib surface and excludes lung and heart. In general, the Chest wall CTV should not cross midline. This Chest wall PTV Eval is the structure used for DVH constraints and analysis and not for beam aperture generation.

#### Regional nodal target volumes

- *Supraclavicular CTV*: Based on consensus definitions from RTOG Breast Cancer Atlas. Superior extent typically is immediately below the caudal edge of the cricoid; medially excludes thyroid, trachea, and esophagus. The lateral border extends to the lateral edge of the sternocleidomastoid muscle superiorly and the clavicle at its more inferior extent, and the inferior border extends to the caudal aspect of the clavicular head.
- *Supraclavicular PTV*: Supraclavicular CTV + 5 mm margin in all directions. The following structures should be excluded from the Supraclavicular PTV to minimize excess dose to normal tissues: ipsilateral thyroid, trachea, esophagus, and ipsilateral lung. This means that some or all of the medial border of the Supraclavicular CTV and PTV will be similar. The Supraclavicular PTV should exclude the vertebral body.
- *Axillary CTV*: The extent of axilla to be targeted for regional nodal irradiation will depend on the extent of axillary surgery performed. The axillary CTV consists of the portion of the axilla that remains "undissected." If an axillary node dissection has been done prior to radiotherapy, the inferior border of the axillary CTV will generally be the most superior (or cephalic) extent of the dissection (i.e., radiation need only be delivered to the undissected axilla). In rare cases, such as a high proportion of nodes involved, treatment will be directed at the dissected axilla and included in this volume at the discretion of the treating physician. Review of the operative report, postoperative changes on the planning CT, and discussion with the patient's surgeon can be used for determining the most cephalic extent of the dissection and inferior border of the Axillary CTV. Axillary dissection typically removes level 1–2 axillary nodes, so that the Axillary CTV in these cases is expected to include level 3. When a sentinel node biopsy alone is done without completion axillary dissection, the axillary CTV will then include all 3 levels of the axilla as all three levels are "undissected." The consensus definitions for anatomical borders of the axillary levels are from the RTOG Breast Cancer Atlas:  
<http://www.rtog.org/CoreLab/ContouringAtlases/BreastCancerAtlas.aspx>
- *Axillary PTV*: Axillary CTV + 5 mm. The ipsilateral lung should be excluded from the Axillary PTV. This means that some or all of the medial border of the Axillary PTV can be similar to the Axillary CTV.
- *Internal mammary node (IMN) CTV*: Includes the internal mammary/thoracic vessels extending from the first to third intercostal spaces on the ipsilateral side regardless of whether or not they will be targeted.
- *Internal mammary node (IMN) PTV*: The IMN CTV + 5 mm medially, laterally, superiorly, and inferiorly. In order to minimize excess normal tissue irradiation, no additional expansion of the IMN CTV into the lung or heart should be done for the IMN PTV. The deep edge for the IMN PTV will be similar to the IMN CTV. No anterior expansion of the CTV into the chest wall or breast

volumes will be done. Treatment of this structure is optional and will be included at the discretion of the treating physician.

#### *Treatment planning*

CT-based planning with tissue inhomogeneity correction is required. *IMRT or 3D-CRT planning techniques are permitted.*

The following definitions and conditions are applied concerning IMRT in this protocol:

1. The treatment plan will be considered IMRT for the purposes of this protocol if an inverse planned optimization is used to determine the beam weights to meet the target and critical structure dose-volume constraints.
2. The plan generated by direct aperture optimization that employs an inverse planning algorithm is considered as IMRT when the target and critical structure dose-volume constraints are met and at least 3 apertures for each beam direction are used.
3. If IMRT is combined with the standard open medial and lateral tangential fields for whole breast irradiation, the IMRT beam should deliver > 50% of the total number of monitor units for the beam orientation.
4. If an IMRT plan is used with another IMRT plan, forward-planning photon beams, and/or electron beam, the 3D composition dose distribution and DVHs should be generated.
5. All standard IMRT planning and delivery systems using MLC (step-and-shoot, dynamic MLC, slide-and-shoot, VMAT, tomotherapy) are allowed and classified as IMRT as long as target and critical structure dose-volume constraints are met.
6. IMRT planning and delivery systems using physical beam-intensity compensators designed by an inverse algorithm to modulate beam intensity so that the required dose constraints are met are also accepted as IMRT.
7. The patient-specific pre-treatment QA measurement is required prior to the first treatment for an IMRT plan.

All plans that do not fit into the above definitions and conditions are classified as 3DCRT plans. Specifically, the plans generated using forward-planning methods or segmental techniques such as "field-in-field" to meet dose-volume constraints are considered as 3DCRT plans. These forward-planned or segmental treatment techniques are those intended to mainly improve the uniformity of the dose distribution but not to produce steep dose gradients to protect critical structures (e.g., heart or lung).

The plans with the number of apertures < 3 for each beam direction are considered 3DCRT plans even if they were generated with inverse planning algorithms

#### *Whole breast plus boost radiation therapy*

The Breast PTV is used to generate the beam apertures with an additional margin to take into account penumbra. Fields should include all of the Breast PTV and boost PTV. The aperture margin generally needed beyond the PTV is 5 mm. The goals of treatment planning are to encompass the breast PTV and minimize inclusion of the heart and lung. Field arrangements for 3DCRT and IMRT of the Breast PTV are at the discretion of the treating physician. Multiple beam arrangements are to be designed during the treatment planning process to produce an optimal plan that meets the dose-volume constraints on the Breast PTV and normal tissues outlined below.

The optional lumpectomy boost may be given by either electron beam or photon beams using either 3DCRT or IMRT. A composite dose distribution and DVHs that include whole breast irradiation using either IMRT or 3DCRT and lumpectomy cavity boost using electron beams, IMRT or 3DCRT must be completed. Simultaneous integrated boost using IMRT is not allowed. Brachytherapy boost is not allowed.

Boost radiation, if administered, must be planned from the initial CT for radiation planning. Changes in patient positioning for the boost are not allowed. If electron boost is used, there must be adequate dosimetric coverage of the Lumpectomy PTV Eval. Bolus may not be used at any time for patients treated with breast conserving surgery.

#### *Chest wall with or without reconstruction radiation therapy*

The goals of treatment planning are to encompass the Chest wall PTV (and regional node targets) and minimize inclusion of the heart and lung. Field arrangements for 3DCRT and IMRT are at the discretion of the treating physician. Multiple beam arrangements that use photons alone of various or mixed energies or in combination with electrons are to be designed during the treatment planning process to produce an optimal plan that meets the dose-volume constraints on the Chest wall PTV and normal tissues outlined below.

In those cases where an expander is in place for purposes of breast reconstruction, there can be a metal port that will need to be taken into account in the radiation treatment planning. Every attempt should be made to acquire the correct density of the expander port so correct modeling can be accomplished. Beam arrangements are to be designed in these cases so that the dose to the chest wall is considered "Per Protocol" or "Variation Acceptable" on DVH analysis.

The treating physician may optionally elect to deliver a chest wall boost. Boost radiation must be planned from the initial CT for radiation planning. A composite dose distribution and DVHs that include chest wall irradiation using either IMRT or 3DCRT and chest wall boost using electron beams, IMRT or 3DCRT must be completed. Simultaneous integrated boost using IMRT is not allowed. Brachytherapy boost is not allowed. If a mastectomy scar boost is used, the dose will be 1068cGy in 4 fractions of 267cGy. There must be adequate dosimetric coverage of the Mastectomy Scar PTV Eval on the plan composite dose volume analysis.

#### **Regional nodal radiation therapy**

The goals of treatment planning are to encompass the supraclavicular, undissected axillary and internal mammary node (optional) targets with the Breast PTV or Chest wall PTV, depending upon the type of surgery performed, and minimize inclusion of the heart and lung. Field arrangements for 3D conformal and IMRT are at the discretion of the treating physician. Multiple beam arrangements are to be designed during the treatment planning process to produce an optimal plan that meets the dose-volume constraints on the supraclavicular, axillary, and internal mammary node targets with the Breast or Chest wall PTV and normal tissues outlined below. In particular, for inclusion of the internal mammary nodes with either the chest wall or breast, there are multiple known field arrangement methods, (e.g., partially wide tangents, combined photon and electron fields, "Danish Technique," etc.) These or any other treatment approach is permissible. Inclusion of the internal mammary nodes will be optional and left to the discretion of the treating physician.

Treatment plans must meet Dose Volume Constraints for the contoured targets and normal structures. Various treatment approaches may be used to develop treatment plans and a composite plan including boost plans must be generated.

### **Required dose-volume histogram (DVH) analysis**

The composite treatment plan for the whole breast with boost and regional nodal irradiation or chest wall and regional nodal irradiation must be done prior to the start of irradiation. All maximum doses should be defined in one dose calculation voxel, e.g., 3x3x3 mm or 3 mm^3.

#### **Chest wall or breast:**

- $\geq 95\%$  of the Chest wall or Breast PTV Eval will receive  $\geq 95\%$  (38 Gy) of the chest wall or breast prescribed dose of 4005 cGy.
- $\leq 50\%$  of the volume of Chest wall or Breast PTV Eval will receive  $\geq 44$  Gy when a boost is included in the composite plan DVH
- Maximal point dose (defined as dose to  $>0.1\text{cc}$ ) within irradiated tissue:
  - when *photons only* are used for a composite plan that includes the Chest wall or Breast PTV Eval +/- IMN PTV:  $\leq 115\%$  of the prescription chest wall or whole breast dose to  $>0.1\text{cc}$  of tissue.
  - when *electron and photons* are mixed for a composite plan that includes the Chest wall or Breast PTV Eval +/- IMN PTV:  $\leq 130\%$  of the prescription Chest wall or whole breast dose to  $>0.1\text{cc}$  of tissue

The Compliance Criteria for Chest wall **boost** are:

- **Per Protocol:**  $\geq 95\%$  of the Mastectomy Scar PTV Eval will receive  $\geq 4819$  cGy which is 95% of the cumulative boost prescribed dose of 5073 cGy
  - **Variation Acceptable:**  $\geq 90\%$  of the Mastectomy Scar PTV Eval will receive 4565 cGy which is 90% of the cumulative boost prescribed dose of 5073 cGy
- **Per Protocol:**  $\leq 5\%$  of the Mastectomy Scar PTV Eval will receive  $\geq 5580$  cGy which is 110% of the boost prescribed dose of 5073 cGy
  - **Variation Acceptable:**  $\leq 10\%$  of the Mastectomy Scar PTV Eval will receive  $\geq 5580$  cGy which is 110% of the boost prescribed dose of 5073 cGy
- **Per Protocol:** Maximal point dose will be  $\leq 534$  cGy which is 115% of the boost prescribed dose of 5073 cGy
  - **Variation Acceptable:** Maximal dose point is  $\leq 6088$  cGy which is 120% of the boost prescribed dose of 5073 cGy

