#### **E. Description, Risks and Justification of Procedures and Data Collection Tools:**

Adjuvant radiation will last 3-4 weeks (15 treatments +/- 4 additional fractions as a boost). Radiation should commence within 180 days of the date of primary surgery. Women will then be followed in accordance with the standard of care for node-positive breast cancer. Information pertaining to the primary and secondary endpoints will be collected at follow-up visits with study clinicians at 6, 12, 36, and 60 months.

Treatment of the internal mammary nodes will be left to the discretion of the treating physician based on clinical indication, practice pattern, and assessment of dose to the heart and underlying lung. Inclusion of internal mammary nodes is optional, though their inclusion or exclusion from the treatment field should be recorded.

Four additional fractions (a “boost” or “cone down”) to areas deemed to be at particularly high risk of recurrence (generally the lumpectomy bed or chest wall scar) may be added at the end of the radiation course at the discretion of the treating physician. Fraction size for the boost treatment will continue at 267 cGy for an additional 1068cGy in four fractions. The exact site, dose, fractionation, and technique (i.e., IMRT, 3D, en face, etc.) should be recorded.

Routine follow-up visits will be performed in accordance with routine standard of care practice and as clinically indicated; however visits before radiation (baseline), and at 6, 12, 36, and 60 months will include a protocol-mandated history and physical exam to include toxicity grading by the physician as well as quality of life questionnaires by the patient. Patients may see study or other oncologic clinicians in between these intervals for follow-up, though toxicity data collection will not be required at these visits. Mammography for any remaining intact breast should be performed annually or as clinically indicated (at the University of Colorado Denver, this is typically six months post radiation then annually or as Bi-RADS indicated). Study clinicians will document data such as functional status (KPS/ECOG), evidence of, and CTCAE grading of any apparent treatment related toxicity. Lymphedema measurements will be performed at these visits. Shoulder mobility assessment will also be performed at these visits.

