#### **Lumpectomy PTV Eval:**

- $\geq 95\%$  of the Lumpectomy PTV Eval will receive  $\geq 4819$  cGy which is 95% of the cumulative boost prescribed dose of 5073 cGy
- $\leq 5\%$  of the Lumpectomy PTV Eval will receive  $\geq 5580$  cGy which is 110% of the boost prescribed dose of 5073 cGy
- Maximal point dose will be  $\leq 5834$  cGy which is 115% of the boost prescribed dose of 5073 cGy

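### For photon-only boosted plans, the composite maximum-dose cap (115% of 4005 cGy) lies below the dose that the lumpectomy and Per Protocol chest wall boost criteria require, and the cap's scope is not stated

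*Combined protocol and SAP*

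**What the plan says.** All references are to the combined protocol and SAP.

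- **Base dose.** Under Chest wall or breast, the coverage criterion is set as a percentage "of the chest wall or breast prescribed dose of 4005 cGy".
- **Boost.** The section on procedures and data collection tools (the first of two lettered E) states: "Fraction size for the boost treatment will continue at 267 cGy for an additional 1068cGy in four fractions". The cumulative dose is 5073 cGy.
- **Cap.** Under Chest wall or breast, the maximal point dose in irradiated tissue may not exceed 115% (photons only) or 130% (electrons and photons mixed) "of the prescription chest wall or whole breast dose to" more than 0.1 cc. The photons-only bullet applies when photons alone "are used for a composite plan that includes the Chest wall or Breast PTV Eval +/- IMN PTV"; the mixed bullet describes its plan in the same terms.
- **Composite.** Under Regional nodal radiation therapy, "a composite plan including boost plans must be generated", and meeting the dose-volume constraints is mandatory. The breast and chest wall planning sections each require a composite dose distribution that contains the boost when one is given. The DVH section opens with "The composite treatment plan for the whole breast with boost and regional nodal irradiation".
- **Photon boosts.** For the breast, "The optional lumpectomy boost may be given by either electron beam or photon beams using either 3DCRT or IMRT". The chest wall section also lists IMRT and 3DCRT as boost techniques.
- **Boost coverage.** Under Lumpectomy PTV Eval, at least 95% of the volume must receive 4819 cGy, "which is 95% of the cumulative boost prescribed dose of 5073 cGy". There is no second tier. The chest wall boost has the same figure as Per Protocol, and a Variation Acceptable tier of at least 90% of the volume at 4565 cGy.
- **Boost upper limits.** A volume limit is set at 5580 cGy, and maxima are set at 5834 cGy (lumpectomy) and 6088 cGy (chest wall, Variation Acceptable).

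**The concern.** The cap is a percentage of the base dose, but the plan it is applied to is a composite that elsewhere must contain the boost. The boost criteria are percentages of the higher cumulative dose. If both sets apply to the same tissue, a ceiling may lie below a required minimum.

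The boost volumes do lie within the capped region. Under Breast volumes, the breast CTV is to include the lumpectomy CTV. Under Chest wall target volumes post-mastectomy, the scar PTV Eval is to stay inside the chest wall PTV Eval.

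At stake is whether the planning limits can be followed as written, and whether all participating sites apply the same hot-spot limit to boosted patients. The trial's primary objective is safety and tolerability, so the limit on high-dose regions should have one meaning. The Data Analysis Plan also lists treatment-delivery compliance among the contents of the initial treatment report. If DVH limits are scored there, the score depends on which limit is taken to govern.

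**Working it through.** **Inputs and the plan's own figures**

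- Base: 15 × 267 = 4005 cGy. Boost: 4 × 267 = 1068 cGy. Cumulative: 4005 + 1068 = 5073 cGy, as stated.
- 95% × 5073 = 4819.35 (printed 4819).
- 90% × 5073 = 4565.7 (printed 4565).
- 110% × 5073 = 5580.3 (printed 5580).
- 115% × 5073 = 5833.95 (printed 5834 for the lumpectomy boost).
- 120% × 5073 = 6087.6 (printed 6088).
- 115% × 4005 = 4605.75. The protocol prints 4606 for this product under Supraclavicular (SCV).

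These all reproduce to rounding. The chest wall boost Per Protocol maximum is printed as 534 cGy but described as 115% of 5073. That is a separate misprint, and nothing below depends on it.

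**The caps in cGy**

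- Photons only: 1.15 × 4005 = 4605.75.
- Mixed: 1.30 × 4005 = 5206.5.

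**Boost figures against the caps**

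| Boost figure | cGy | As % of 4005 | Minus photon cap (4605.75) | Minus mixed cap (5206.5) |
|---|---|---|---|---|
| Coverage: lumpectomy; chest wall Per Protocol | 4819 | 120.3 | +213 | −387.5 |
| Coverage: chest wall Variation Acceptable | 4565 | 114.0 | −41 | −641.5 |
| Cumulative prescription | 5073 | 126.7 | +467 | −133.5 |
| Volume limit | 5580 | 139.3 | +974 | +373.5 |
| Lumpectomy maximum | 5834 | 145.7 | +1228 | +627.5 |
| Chest wall maximum, Variation Acceptable | 6088 | 152.0 | +1482 | +881.5 |

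**Photon-only plans.** A coverage dose above the cap cannot be delivered to 95% of a volume while the cap holds, unless that volume is negligible. The cap allows at most 0.1 cc above it, so the boost PTV Eval could be no larger than 0.1 / 0.95 = 0.105 cc. For comparison, the lumpectomy expansions of 1 cm and 7 mm around a single point give a sphere of radius 1.7 cm, which is 20.6 cc before trimming to the PTV Eval. The 0.1 cc allowance therefore does not remove the conflict.

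**Chest wall Variation Acceptable.** The coverage dose is 40.75 cGy under the cap, a window of 40.75 / 4605.75 = 0.9%. Both criteria can be met on paper, but only by holding the boost volume below its 5073 cGy prescription.

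**Mixed plans.** The cap is 387.5 cGy above the coverage dose, so both can be met. It is 5206.5 / 5073 = 102.6% of the cumulative prescription and lies below all three boost-specific upper limits. If the cap governs, those limits never come into play; if they govern, the cap does not apply to boosted tissue.

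**The case against.** The strongest reply is that the caps were meant for the base plan with or without the internal mammary nodes, and that the boost criteria govern the boost volume. Several features of the text support this.

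- The cap bullets name the optional internal mammary volume and do not name the boost.
- The bullet just above them, on the volume receiving 44 Gy, says expressly that it concerns a composite with a boost. That suggests the boost is not assumed in every bullet.
- The protocol does not use the word composite only for boosted plans. The opening sentence of the DVH section goes on to chest wall with nodal irradiation and names no boost there. Item 4 of the IMRT definitions requires composite dose distributions for combined beams generally.
- Boost maxima have their own lists, referenced to 5073 cGy.
- The literal reading would defeat a photon lumpectomy boost that the protocol permits.

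This reading is coherent and may be what was intended, but it is nowhere stated. The nodal section requires a composite that includes boost plans, the breast and chest wall sections say the same, and the 44 Gy bullet shows a boost being counted in this DVH. The objection therefore makes the intent uncertain but does not remove the conflict in the text.

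A reader might also infer more than the documents support:

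- **That no photon-only boosted plan can comply.** The chest wall Variation Acceptable tier is an exception, though a narrow one.
- **That mixed plans are impossible too.** They are not. Two upper limits on the same tissue can both be met, because the lower one binds.
- **That a compliance rate can be predicted.** The documents do not give the share of patients boosted or the technique used. Nor do they say that hot-spot limits enter the compliance rate, which is described in relation to the prescription.

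**Conclusion.** The concern stands in a limited form. On the plain text, a photon-only composite with a lumpectomy boost, or with a chest wall boost judged at the Per Protocol coverage tier, cannot meet both the 4606 cGy cap and the 4819 cGy coverage requirement. The shortfall is 213 cGy. The chest wall Variation Acceptable coverage tier fits under the cap by 41 cGy. For mixed electron and photon plans there is no impossibility, but the governing maximum is unclear, because the boost-specific limits exceed the 5206.5 cGy cap by 373.5 to 881.5 cGy.

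This rests on two readings: that the composite in the cap bullets is the boosted composite required elsewhere, and that the reference dose is 4005 cGy. The second is explicit. The first is the plain reading, but the reference to the internal mammary volume alone leaves the base-plan reading open.

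The arithmetic of the individual limits is sound; the fault is that two mandatory figures are not reconciled. It does not alter the primary endpoint, its decision rule or the analysis population, since all eligible patients who begin protocol treatment are analysed.

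**What to change.** Reconcile the breast, chest wall and nodal planning sections with the DVH criteria for the chest wall or breast and the lumpectomy PTV Eval. The revised text should state:

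1. which plan or which tissue the 115% and 130% caps cover; and
2. which maximum governs a composite that includes a boost, for photon-only and for mixed plans.

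The choice of limits belongs to the sponsor, and this review does not propose one. The same reading should then be applied wherever DVH compliance is scored, including any use of it in the initial treatment report described in the Data Analysis Plan.

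The cost is a wording change confined to the planning and DVH text, with no new patients, procedures or assessments. Plans already scored may need re-scoring from stored DVHs.

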A non-inferiority margin of 10% was chosen after extensive consultation with multiple radiation oncologists. Note this margin is an absolute difference between the toxicity event rate of standard treatment (assumed to be 40%) and that of proposed treatment, where a higher rate indicates treatment is more toxic. The sample size calculation is based powering the study with 80% power and 5% significance level. The sample size is dependent on the actual absolute difference between the toxicity event rate of standard treatment and that of the proposed treatment. When it is assumed that the actual toxicity event rate of proposed treatment is 2% lower (absolute difference) than that of standard care, a total number of 106 patients accomplishes abovementioned power. If less than 44 patients out of 106 are observed to have adverse event, we will conclude that the proposed treatment is non-inferior to standard treatment. Assuming an estimated drop-out rate of 5% of patients lost to follow-up, the calculated total number of patients will be inflated accordingly to 112.

The initial treatment report will contain the following:

1. study accrual rate;
2. tabulation of all cases entered, and any patients excluded from the analysis with reasons for exclusion;
3. distribution of important prognostic baseline variables;
4. compliance rates of treatment delivery with respect to the protocol prescription;
5. observed results with respect to the primary endpoint described above.

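### The Per Protocol maximal point dose for the chest wall boost is printed as 534 cGy, but 115% of 5073 cGy is 5834 cGy

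*Combined protocol and SAP*

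**What the plan says.** The section on required dose-volume histogram analysis, under Chest wall or breast, sets two-tier compliance criteria (Per Protocol and Variation Acceptable) for the chest wall boost. For the maximal point dose, the Per Protocol tier reads "Maximal point dose will be $\leq 534$ cGy which is 115% of the boost prescribed dose of 5073 cGy" and the Variation Acceptable tier reads "Maximal dose point is $\leq 6088$ cGy which is 120% of the boost prescribed dose of 5073 cGy".

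The same list sets Per Protocol coverage: at least 95% "of the Mastectomy Scar PTV Eval will receive $\geq 4819$ cGy which is 95% of the cumulative boost prescribed dose of 5073 cGy".

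The next block, Lumpectomy PTV Eval, states the same 115% rule on the same base for the lumpectomy boost: "Maximal point dose will be $\leq 5834$ cGy which is 115% of the boost prescribed dose of 5073 cGy".

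The section on chest wall radiotherapy with or without reconstruction fixes the boost itself: "If a mastectomy scar boost is used, the dose will be 1068cGy in 4 fractions of 267cGy". The section on regional nodal radiotherapy adds the general requirement "Treatment plans must meet Dose Volume Constraints for the contoured targets and normal structures".

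**The concern.** The sentence gives a dose and says what percentage of the prescription that dose represents, and the two disagree by a factor of about eleven. As a maximum, 534 cGy is physically impossible for these plans. It equals two 267 cGy fractions, half of the boost alone, and it lies far below the minimum dose that the same list requires across nearly all of the scar volume.

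The line is a numeric threshold in the criteria used to score treatment plans, so it is not background text. A literal reading would reject no plan, because the Variation Acceptable maximum of 6088 cGy still applies. It would, however, empty the Per Protocol tier and move every boosted chest wall plan down one tier on this item. The two tiers exist to distinguish plans within 115% from plans between 115% and 120%, and that distinction would be lost. The initial treatment report described in section F, Data Analysis Plan, is to include "compliance rates of treatment delivery with respect to the protocol prescription", but the plan does not say whether these tiers feed that figure.

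**Working it through.** **Inputs**

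- Base prescription: 4005 cGy in 15 fractions (section C, schema), i.e. 267 cGy per fraction.
- Scar boost: 1068 cGy in 4 fractions of 267 cGy (Chest wall with or without reconstruction).
- Cumulative boost dose: 5073 cGy (Chest wall or breast).

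**Step 1: confirm the base.** 15 × 267 = 4005 and 4 × 267 = 1068. Their sum is 4005 + 1068 = 5073 cGy, as printed.

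**Step 2: try to reproduce the stated limit.** 1.15 × 5073 = 5833.95, which rounds to 5834 cGy. The printed 534 cGy is not reproduced: 534 / 5073 = 10.5%, and 534 / 267 = 2 fractions.

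**Step 3: try other bases.** 115% of the boost alone is 1.15 × 1068 = 1228 cGy. 115% of the base prescription is 1.15 × 4005 = 4606 cGy. Neither gives 534.

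**Step 4: check the neighbouring limits.** Five blocks (Chest wall or breast, Lumpectomy PTV Eval, Supraclavicular, Axillary, Internal mammary) print 12 limits in cGy as a stated percentage of 4005 or 5073.

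| Block | Rule | Printed (cGy) | Computed (cGy) | Absolute difference |
|---|---|---|---|---|
| Chest wall boost | 95% of 5073 | 4819 | 4819.35 | 0.35 |
| Chest wall boost | 90% of 5073 | 4565 | 4565.70 | 0.70 |
| Chest wall boost | 110% of 5073 (Per Protocol) | 5580 | 5580.30 | 0.30 |
| Chest wall boost | 110% of 5073 (Variation Acceptable) | 5580 | 5580.30 | 0.30 |
| Chest wall boost | **115% of 5073** | **534** | **5833.95** | **5299.95** |
| Chest wall boost | 120% of 5073 | 6088 | 6087.60 | 0.40 |
| Lumpectomy | 95% of 5073 | 4819 | 4819.35 | 0.35 |
| Lumpectomy | 110% of 5073 | 5580 | 5580.30 | 0.30 |
| Lumpectomy | 115% of 5073 | 5834 | 5833.95 | 0.05 |
| Supraclavicular | 115% of 4005 | 4606 | 4605.75 | 0.25 |
| Axillary | 110% of 4005 | 4406 | 4405.50 | 0.50 |
| Internal mammary | 110% of 4005 | 4406 | 4405.50 | 0.50 |

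Eleven of the 12 agree to within 1 cGy. Only the chest wall 115% limit does not.

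**Step 5: size of the effect on scoring.** The printed limit is 5834 − 534 = 5300 cGy too low. The band that the two tiers should separate is 6088 − 5834 = 254 cGy wide. With 534 in place, a plan with a maximum at or below 5834 cGy and a plan inside that band receive the same score, Variation Acceptable.

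**The case against.** The arithmetic is not in dispute. Four points can be made against giving it weight.

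- **It may be an extraction artefact.** 534 is 5834 with its second digit missing, and the text was machine-read from a PDF. This stands as a caveat, since the text alone cannot settle it. Against it, the sentence shows no gap or redaction, and the other 11 percentage-derived limits came through intact.

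- **The error corrects itself.** The same sentence gives the 115% rule, the next line gives 6088 cGy for 120%, and the lumpectomy block prints 5834 cGy. A competent planner would see that 534 is impossible and infer the right value. This is fair and is why the point is minor. The scoring consequences above follow only if someone applies the number literally, and nothing in the documents shows that anyone did.

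- **Other caps may bind first.** The same section caps the maximal dose of a composite plan at 115% (photons only) or 130% (mixed electrons and photons) of the chest wall dose, about 4606 or 5207 cGy on 4005. If these applied to boosted composites, neither 5834 nor 6088 would bind. The text is not clear on this. For photons-only plans that reading is hard to sustain, because 4606 cGy is below the 4819 cGy coverage the boost requires. In any case it does not change what this item's two tiers say.

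- **The reach is narrow.** The boost is optional, the sentence saying that plans must meet the constraints sits in the regional nodal section, and for expander cases the protocol accepts either tier. All of this is true. It limits the consequence but does not make the number right.

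**Conclusion.** The point holds, as a minor error. The Per Protocol maximal point dose for the chest wall boost is wrong as printed: it should be 5834 cGy, not 534 cGy. Followed literally, it makes the Per Protocol tier unattainable for every boosted chest wall plan on this one item and removes the distinction across the 254 cGy band between 115% and 120%.

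The effect is confined to compliance scoring and the hot-spot limit for optional chest wall boosts. The composite toxicity endpoint, the sample size of 106 (112 with drop-out) and the decision rule of fewer than 44 events are untouched.

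The conclusion that the text is internally inconsistent rests on arithmetic alone. The conclusion that the protocol itself carries the error assumes that the digit was not lost in reading the PDF.

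**What to change.** Check the source PDF first. If it prints 5834, nothing needs to change. If it prints 534, replace it with 5834 cGy in the chest wall boost compliance criteria, matching the lumpectomy block, by erratum or in the next amendment. The cost is one number, with no change to treatment, endpoint, sample size or decision rule.
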